5.4.4. Safety Endpoints

Safety endpoints consist of the incidences of treatment emergent adverse events (TEAEs), serious adverse events (SAEs) and adverse events (AEs) leading to discontinuation, follow-up-emergent adverse events (FEAEs) during Study Period IV, vital signs (blood pressure, pulse, and body temperature), weight, suicidal ideation and behaviors assessed by solicited questioning using the Columbia-Suicide Severity Rating Scale (C-SSRS), electrocardiograms (ECGs), and laboratory measures (chemistry, hematology, and urinalysis).

5.4.5. Immunogenicity Endpoints

Immunogenicity endpoints consist of the incidences of anti-drug antibodies (ADAs) in all trial participants at baseline (pre-existing ADAs), and in all trial participants at post-baseline (treatment emergent ADAs). An additional endpoint is the incidence of neutralizing antibodies (NAbs) present in those trial participants with ADAs.

The definition of baseline is as follows:

EM patients: CGAN Visit 3

CM patients: CGAP Visit 3

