For EM patients' analysis, baseline is Study CGAP Visit 3 (Study CGAN Visit 12) assessment, unless otherwise specified with some exception (e.g., immunogenicity analysis). If baseline data is not available at Study CGAP Visit 3 (e.g., height), then baseline assessment of CGAN will be used.

Additional exploratory analyses of the data will be conducted as deemed appropriate.

Statistical analysis of this study will be the responsibility of Eli Lilly and Company or designee. SAS[®] software will be used to perform most or all statistical analyses.

Post-Treatment Emergent and Follow-up Emergent are used interchangeably in this study.

Summary tables will display each arm (EM120, EM240, CM120, CM240). In addition, if the summary is sorted by total (LY_ALL), then the "LY_ALL" will be shown (e.g. summary of TEAE, summary of pre-existing condition).

The measurements of PGI-I, PGI-S, MSQ, MIDAS PSMQ-M, or HCRU will be used if they are taken on the same day of the injection date even if the measurements are after injection timing. But if it is after the injection day, then it will be excluded.

For PGI-I, PGI-S, MSQ, MIDAS, and MHD related analysis with repeated measurement in SP III (continuous and binary outcomes), "overall (month 1-12)" will be shown for treatment comparisons at the final DBL.

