5.5.1.4. Baseline and Post-Baseline Definition

[Table CGAP. 5.4](#) describes the rules for determining the patient population and baseline and post-baseline observations for each study phase and type of analysis. When “last of Visit x-x” is used in the table, the last nonmissing observation obtained in the visit interval will be used.

Table CGAP. 5.4 Patient Population with Baseline and Post-Baseline Definitions by Study Period and Type of Analysis

Study Period/Analysis	Patient Population	Baseline Observation	Post-baseline Observation(s)
Study Period III			
Efficacy analyses	ITT Population with a baseline and at least 1 post-baseline observation	Visit 3	All Visits 3.01–16
Mean change from baseline in the number of migraine headache days	PPS Population with a baseline and at least 1 post-baseline observation	Visit 3	All Visits 3.01–16
Quality of Life analyses	ITT Population with a baseline and at least 1 post-baseline observation	Visit 3	All Visits 3.01–16
TEAEs	Safety Population	EM: CGAN Visit 1 – CGAP Visit 3 CM: All Visits 1–3. Pre-existing condition that is still ongoing at Visit 1 should be evaluated as baseline values.	All Visits 3.01–16
Serious Adverse Events, Discontinuations due to Adverse Events	Safety Population	NA	All Visits 3.01–16
C-SSRS categorical analyses	Safety population with a baseline and at least 1 post-baseline C-SSRS assessment	EM: Recent History: CGAP Visit 3 All Prior History: All CGAN Visits 1-12 including lifetime ^a CM: Recent History: All CGAP Visits 1–3 excluding lifetime ^a	All Visits 3.01–16

Study Period/Analysis	Patient Population	Baseline Observation	Post-baseline Observation(s)
		All Prior History: All CGAP Visits 1 – 3 including lifetime ^a	
C-SSRS categorical analyses for improvement	Safety population with a baseline and at least 1 post-baseline C-SSRS assessment	EM: Visit 3 CM: Last of CGAP Visit 1-3.	Last of 3.01–16
Treatment emergent abnormal laboratory values	Safety Population with normal laboratory values at all nonmissing baseline visits (with respect to direction being analyzed) and who have at least 1 post-baseline observation	EM: Visit 3 CM: All Visits 1–3	All Visits 3.01–16
Treatment emergent immunogenicity	Safety Population. ADA follow-up cohort (See Section 5.5.12.1.6)	EM (LY120/LY120, LY240/LY240): CGAN Visit 3 EM (PLA/LY120, PLA/LY240): CGAP Visit 3 CM: Visit 3	All Visits 3.01–16

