Treatment emergent changes in vital signs, weight, and ECGs	Safety Population with a baseline and at least 1 post-baseline observation	EM: Visit 3 CM: Low: Minimum value from Visits 1–3 High: Maximum value from Visits 1–3	Low: Minimum value from Visits 3.01–16 High: Maximum value from Visits 3.01–16
Continuous safety analyses	Safety Population with a baseline and at least 1 post-baseline observation	EM: Visit 3 CM: Last of Visits 1–3	Scheduled visits: 3 < Visits ≤ 16
Study Period III and IV combined			
Efficacy analyses	ITT Population with a baseline and at least 1 post-baseline observation	Visit 3	All Visits 3.01-18
Quality of Life analyses	ITT Population with a baseline and at least 1 post-baseline observation	Visit 3	All Visits 3.01-18

Study Period/Analysis	Patient Population	Baseline Observation	Post-baseline Observation(s)
Continuous safety analyses	Safety Population with a baseline and at least 1 post-baseline observation	EM: Visit 3 CM: Last of Visit 1- 3	All Visits 3.01-18
Treatment emergent immunogenicity	ADA follow-up cohort (See Section 5.5.12.1.6)	EM (LY120/LY120, LY240/LY240): CGAN Visit 3 EM (PLA/LY120, PLA/LY240): CGAP Visit 3 CM: Visit 3	All Visits 3.01–18
Study Period IV			
Continuous safety analyses – change from baseline to LOCF endpoint (ANCOVA)	Post-treatment Population with a baseline and at least one post-baseline observation	EM: Last of Visits 3-16 CM: Last of Visits 1-16	Last Visit: 16.01-18
FEAEs	Post-treatment Population	EM: All Visits in CGAN Visit 1 - 16. CM: All Visits 1- 16. Pre-existing condition that is still ongoing at Visit 1 should be evaluated as baseline values.	All Visits 16.01–18
Serious Adverse Events, Discontinuations due to Adverse Events	Post-treatment Population	NA	All Visits 16.01–18
Follow-up emergent abnormal laboratory values	Post-treatment Population with normal laboratory values at all nonmissing baseline visits (with respect to direction being analyzed) and who have at least 1 post-baseline observation	EM: All Visits 3- 16 CM: All Visits 1- 16	All Visits 16.01–18
Follow-up emergent changes in vital signs, weight and ECGs	Post-treatment Population with a baseline and at least 1 post-baseline observation	EM: Low: Minimum value from Visits 3–16 High: Maximum value	Low: Minimum value from Visits 16.01–18 High: Maximum value from Visits 16.01–18

Study Period/Analysis	Patient Population	Baseline Observation	Post-baseline Observation(s)

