5.5.12.1.6. Immunogenicity

The summary TFLs will be based on 6 arms (LY120/LY120, LY240/LY240, PLA/LY120, PLA/LY240, CM120, CM240). To evaluate the changes in immunogenicity data of

- Anti-LY2951742 Antibody (hereafter, “Anti-Drug Antibody (ADA),”)
- Neutralizing ADA (hereafter, “Neutralizing Antibody” (NAb)) after treatment,

the statistical analyses (Fisher's exact test) are planned for comparison between treatment groups.

The summary (baseline=Visit 3) will be created for

1. SP III (safety population)
2. SP III (ADA follow-up cohort)
3. SP III and SP IV combined (ADA follow-up cohort)

Analysis of each period includes:

- The incidence of “ADA positive (%)” and “ADA positive and NAb Positive (%)” during baseline.
- The incidence of treatment emergent ADA (TE ADA) between treatment groups. The baseline and post-baseline definitions for each study period is shown in [Table CGAP. 5.4](#). Treatment emergent ADA will be defined as any of the following:
 - A negative baseline result and a positive post-baseline ADA result with a titer ≥ 20 . This is also called treatment-induced ADA.
 - A positive baseline result and a positive post-baseline ADA result with a ≥ 4 -fold increase in titers (for example, baseline titer of 10 increasing to ≥ 40 post-baseline). This is called treatment-boosted ADA.
- The incidence of TE-ADA and NAb Positive combined.

Note that TE-ADA can happen at multiple visits during SP III (or SP III and SP IV combined) because the judgement is solely based on comparison between the particular visit and the baseline. (i.e., listings may contain multiple TE-ADA time points, although one TE-ADA point is enough to be considered being TE-ADA subject with that TE-ADA.)

The following will also be created:

- Listing of subjects with TE-ADA at any time during study (SP III and SP IV combined), NAb Status will also be displayed.
- Listing of subjects with ADA detected at any time during study (SP III and SP IV combined) excluding subjects with TE-ADA.
- Listing of subjects with TEAEs of hypersensitivity reactions or injection site reactions or ADA present at any time (SP III, SP IV).

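### SAP 5.4.5 and Table CGAP. 5.4 set different immunogenicity baselines for EM patients who received placebo in CGAN, so baseline ADA prevalence and treatment-emergent ADA in those arms depend on the section followed

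*SAP*

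**What the plan says.** Section 5.4.5 defines the immunogenicity endpoints as ADA at baseline (pre-existing) and ADA "in all trial participants at post-baseline (treatment emergent ADAs"), plus neutralizing antibodies among patients with ADA. For all of these it gives one line for episodic migraine, "EM patients: CGAN Visit 3", with no split by CGAN arm. CM patients take CGAP Visit 3.

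Table CGAP. 5.4 in section 5.5.1.4 does split by CGAN arm. For Study Period III it reads "EM (LY120/LY120, LY240/LY240): CGAN Visit 3 EM (PLA/LY120, PLA/LY240): CGAP Visit 3 CM: Visit 3". The row for Study Periods III and IV combined repeats the split, including "EM (PLA/LY120, PLA/LY240): CGAP Visit 3 CM: Visit 3".

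Section 5.5.12.1.6 introduces its three summaries with "The summary (baseline=Visit 3) will be created for" and names no study. Further down, inside the treatment-emergent ADA item, it says "The baseline and post-baseline definitions for each study period is shown in" Table CGAP. 5.4. The separate item on ADA and NAb positivity at baseline carries no such reference.

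Section 5.5.1 gives the general rule for EM patients: "baseline is Study CGAP Visit 3 (Study CGAN Visit 12) assessment, unless otherwise specified with some exception (e.g., immunogenicity analysis"). It does not say what the immunogenicity exception is.

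**The concern.** CGAN Visit 12 is the same visit as CGAP Visit 3 (SAP 5.1.1). The two candidate baselines are therefore separated by the CGAN treatment phase, during which PLA/LY patients were assigned to placebo. If the earlier date is used for them, antibody changes that arose without galcanezumab can be credited to it. A re-conversion on galcanezumab can also be judged against a positive sample that was no longer current when dosing began.

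ADA development is part of a stated secondary objective. Section 5.5.12.1.6 summarises it in six arms with Fisher's exact tests between groups. For the two PLA/LY arms, the baseline prevalence, the treatment-emergent incidence and any test involving those arms can differ with the section the programmer follows.

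**Working it through.** No sample-size or power figure is involved. The check applies the SAP's own classification rule to titer histories under each baseline.

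**Rule (SAP 5.5.12.1.6).** Baseline negative: a post-baseline visit qualifies if ADA is positive with titer at least 20. Baseline positive: it qualifies if the titer is at least 4 × baseline. One qualifying visit is enough.

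**Post-baseline window (Table CGAP. 5.4).** Visits 3.01–16 for Study Period III and 3.01–18 for the combined periods, all in CGAP.

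**The SAP's own example.** Baseline titer 10 gives a threshold of 4 × 10 = 40. A titer of 40 qualifies and 39 does not, which agrees with the example in the text.

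**Histories.** These are constructed to show how the rule behaves; they are not data. Each threshold is the titer needed to qualify.

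| History | CGAN V3 | CGAP V3 | CGAP post-baseline | Threshold, 5.4.5 | TE-ADA, 5.4.5 | Threshold, Table 5.4 | TE-ADA, Table 5.4 |
|---|---|---|---|---|---|---|---|
| A. PLA/LY, converts on placebo and persists | neg | 20 | 20, 40, 20 | 20 | yes | 4 × 20 = 80 | no |
| B. PLA/LY, rises on placebo and persists | 10 | 40 | 40, 40 | 4 × 10 = 40 | yes | 4 × 40 = 160 | no |
| C. PLA/LY, positive, then negative, then positive on drug | 20 | neg | 20, 40 | 4 × 20 = 80 | no | 20 | yes |
| D. PLA/LY, transient positivity on placebo | neg | 20 | neg, neg | 20 | no | 80 | no |
| E. PLA/LY, first conversion in CGAP | neg | neg | 20, 40 | 20 | yes | 20 | yes |
| F. LY/LY, converts in CGAN and persists | neg | 40 | 40, 80 | 20 | yes | 20 | yes |

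**Treatment-emergent ADA.** The two sections disagree on A, B and C only, all in PLA/LY. A and B are added by 5.4.5 and C is removed by it, so the net direction in a PLA/LY arm is not fixed. D shows that placebo-period positivity alone is not counted under either rule; it must still be present at a qualifying titer in CGAP. F shows that LY/LY is classified identically, because both sections give it CGAN Visit 3. CM patients have CGAP Visit 3 in both.

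**Baseline prevalence.** Patient A is baseline-negative under 5.4.5 and baseline-positive under the table. Patient C is the reverse.

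**Size.** A count needs the number of PLA/LY patients and the rates of histories A to C. SAP 5.2.1 gives about 240 EM patients but no split by CGAN arm, and neither document gives an ADA rate. Purely as an illustration for histories like A, assume 60 to 160 PLA/LY patients and 1% to 10% persistent conversion. The product runs from 60 × 0.01 = 0.6 to 160 × 0.10 = 16 patients, which is too wide to serve as an estimate.

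**The case against.** The best counter-argument is that the intended rule can be recovered. Section 5.5.12 sends safety baselines, antibodies included, to Table CGAP. 5.4, and 5.5.12.1.6 does so again for treatment-emergent ADA. The revision history records that Version 3 introduced the split into the table and lists no change to 5.4.5, which suggests a line left behind. An analyst working from the analysis sections would probably use the split.

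Much of that stands, and it limits the consequence. It does not remove the contradiction. The pointer in 5.5.12 applies unless otherwise specified, and 5.4.5 does specify otherwise. The immunogenicity exception in 5.5.1 fits 5.4.5 as well as it fits the table. The pointer in 5.5.12.1.6 sits within the treatment-emergent item, and the table row is itself labelled for treatment-emergent immunogenicity, so baseline prevalence is left to 5.4.5 and an unlabelled Visit 3.

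A reader might infer three stronger things that the documents do not support.

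- That 5.5.12.1.6 is a third competing rule, setting CGAP Visit 3 for everyone and so losing LY/LY patients who converted on galcanezumab in CGAN. On that reading patient F would need 4 × 40 = 160 and would drop out. But the section refers treatment-emergent ADA to the table, and 5.5.1 names immunogenicity as an exception to the CGAP Visit 3 default. What remains is an imprecise label and a missing pointer for prevalence.
- That patients could be counted as treatment-emergent before receiving any drug. Only CGAP visits after Visit 3 are post-baseline, so a count needs persistence into CGAP.
- That PLA/LY and LY/LY are misclassified in opposite directions. That combines two mutually exclusive readings; neither 5.4.5 nor CGAP Visit 3 for all departs from the table in both groups.

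**Conclusion.** The point holds for the PLA/LY arms. Section 5.4.5 and Table CGAP. 5.4 give them different baselines in current text, and the difference changes both baseline prevalence and treatment-emergent ADA. Following 5.4.5 would attribute persistent placebo-period positivity to galcanezumab and could hide a re-conversion on drug. The contradiction rests on the wording alone and needs no assumption. Its size in patients, and the net direction of any error, cannot be derived from the documents. LY/LY and CM patients are not affected by this conflict. It should be corrected because an objective-level endpoint is ambiguous, but it is a wording alignment with a likely intended answer and does not call the design into question.

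**What to change.** 1. In 5.4.5, replace the single EM line with the split in Table CGAP. 5.4: LY120/LY120 and LY240/LY240 take CGAN Visit 3; PLA/LY120 and PLA/LY240 take CGAP Visit 3. CM stays at CGAP Visit 3. In each arm the baseline then precedes the first galcanezumab dose.
2. In 5.5.12.1.6, replace the unlabelled Visit 3 in the summary line with a reference to the baseline in Table CGAP. 5.4, and state that it governs both baseline ADA/NAb prevalence and treatment-emergent ADA.

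The cost is two lines of SAP text and a check that the immunogenicity programs use the split. No new data are needed, since Table CGAP. 5.4 already relies on the same samples.

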5.4.6. CCI

CCI

5.4.7. Pharmacokinetic Assessment

Serum LY2951742 concentration will be determined in trial participants following LY2951742 administration at specified visits throughout the trial. Pharmacokinetic assessments will be summarized in the PK/PD analysis plan described in the protocol.

5.5. Statistical Analyses

The SAP Version 1 was approved prior to first patient visit and SAP Version 2 prior to the interim database lock. The SAP Version 3 was created after reviewing preliminary analysis results based on SAP Version 2, using the interim database lock. The SAP supersedes the

statistical plans described in the protocol. PK/PD analysis is out of scope in this Section. Detail of the analysis is specified in Section 5.4.6 and Section 5.4.7.

5.5.1. General Considerations

Unless otherwise specified, analyses will be conducted on an intent-to-treat (ITT) population, which will include all patients who are randomized at Visit 3 and receive at least 1 dose of study drug. Patients in the ITT population will be analyzed according to the treatment group to which they are randomized. When change from baseline is assessed, the patient will be included in the analysis only if he/she has a baseline and a post-baseline measurement.

Unless specified otherwise, data will be reported by the following treatment groups.

- EM120: EM patients who are randomized to galcanezumab 120 mg in Study CGAP
- EM240: EM patients who are randomized to galcanezumab 240 mg in Study CGAP
- CM120: CM patients who are randomized to galcanezumab 120 mg in Study CGAP
- CM240: CM patients who are randomized to galcanezumab 240 mg in Study CGAP

For some reports, following groups will be used:

- LY120/LY120: Study CGAN 120 mg galcanezumab with a loading dose/Study CGAP 120 mg galcanezumab with placebo injection for a loading dose
- LY240/LY240: Study CGAN 240 mg galcanezumab/Study CGAP 240 mg galcanezumab
- PLA/LY120: Study CGAN placebo/Study CGAP 120 mg galcanezumab with a loading dose
- PLA/LY240: Study CGAN placebo/Study CGAP 240 mg galcanezumab
- EM_ALL: all EM patients from Study CGAN (= EM120 + EM240)
- CM_ALL: all CM patients started from Study CGAP (= CM120 + CM240)
- LY_ALL: all patients (EM_ALL + CM_ALL)

Frequency tables such as AE or TEAEs will be sorted by total (LY_ALL) in decreasing frequency.

When 4 arms (EM120, EM240, CM120, CM240) are displayed and statistical comparisons are made, then it will be based on (EM120 vs EM240, CM120 vs CM240), unless otherwise specified.

When 3 arms (EM_ALL, CM_ALL, LY_ALL) are displayed and statistical comparisons are made, then it will be based on EM_ALL and CM_ALL, unless otherwise specified.

For efficacy and QoL analysis, descriptive statistics will be used. They will be displayed by 6 arms (LY120/LY120, LY240/LY240, PLA/LY120, PLA/LY240, CM120, CM240). There will be no statistical comparison among arms. In the summary of continuous variables, the mean, standard deviation, standard error, minimum, median, and maximum will be reported.

For efficacy and QoL analysis, in addition to the descriptive statistics, when statistical model is used such as MMRM, GLIMMIX, logistic regression, then 2 arms (CM120, CM240) will be used with statistical comparisons between arms.

For safety analysis, when statistical model is used such as MMRM, or ANCOVA, then 4 arms (EM120, EM240, CM120, CM240) will be used without any statistical comparisons between arms.

For listings, they will be displayed by 6 arms (LY120/LY120, LY240/LY240, PLA/LY120, PLA/LY240, CM120, CM240), unless otherwise specified.

All statistical tests will be conducted at a 2-sided alpha level of 0.05, and 95% confidence intervals will be provided, if appropriate. No adjustments for multiplicity will be applied to any safety or effectiveness analyses.

Change from baseline of continuous variables with repeated measures will be analyzed using a mixed model repeated measures (MMRM) analysis, unless otherwise specified. An MMRM analysis refers to a restricted maximum likelihood (REML)-based, mixed-effects repeated measures analysis using all the longitudinal observations at each post-baseline visit.

For other continuous variables without repeated measures, the change from baseline to LOCF endpoint will be analyzed using an analysis of variance (ANOVA) or ANCOVA model.

Unless otherwise specified, when an ANOVA model or ANCOVA model is used to analyze a continuous efficacy variable, type III sum-of-squares for the least-squares means (LSMean) will be used for the statistical comparisons.

Visit-wise binary efficacy variables will be analyzed using a generalized linear mixed model (GLIMMIX) as pseudo-likelihood-based mixed effects repeated measures analysis for categorical data (MMRM-CAT).

For categorical efficacy variables without repeated measures, comparisons between treatment groups will be performed using logistic regressions.

For other categorical variables without repeated measures, comparisons between treatment groups will be performed using Fisher's exact tests unless otherwise specified. For example,

- Baseline patient characteristics
- Safety measures (including percentages of patients with TEAEs, SAEs, and AEs reported as a reason for discontinuation, as well as those patients who met categorical criteria for changes in vital signs and weight, ECGs, and laboratory tests)

Only scheduled visit data will be available for the following data. In other words, there will be no unscheduled visit data;

- Patient migraine headache data collected by diary
- PGI-S
- PGI-I
- MSQ v2.1
- MIDAS
- PSMQ-M
- HCRU

For EM patients' analysis, baseline is Study CGAP Visit 3 (Study CGAN Visit 12) assessment, unless otherwise specified with some exception (e.g., immunogenicity analysis). If baseline data is not available at Study CGAP Visit 3 (e.g., height), then baseline assessment of CGAN will be used.

Additional exploratory analyses of the data will be conducted as deemed appropriate.

Statistical analysis of this study will be the responsibility of Eli Lilly and Company or designee. SAS[®] software will be used to perform most or all statistical analyses.

Post-Treatment Emergent and Follow-up Emergent are used interchangeably in this study.

Summary tables will display each arm (EM120, EM240, CM120, CM240). In addition, if the summary is sorted by total (LY_ALL), then the "LY_ALL" will be shown (e.g. summary of TEAE, summary of pre-existing condition).

The measurements of PGI-I, PGI-S, MSQ, MIDAS PSMQ-M, or HCRU will be used if they are taken on the same day of the injection date even if the measurements are after injection timing. But if it is after the injection day, then it will be excluded.

For PGI-I, PGI-S, MSQ, MIDAS, and MHD related analysis with repeated measurement in SP III (continuous and binary outcomes), "overall (month 1-12)" will be shown for treatment comparisons at the final DBL.

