4.2. Secondary Objectives

Table CGAP. 4.1 shows the secondary objectives and endpoints of the study. Table CGAP. 4.2 provides definitions for the terms referenced below.

Table CGAP. 4.1 Objectives and Endpoints

Objectives	Endpoints

Primary
 
To evaluate the long-term safety and tolerability of galcanezumab 120 mg/month or 240 mg/month in patients with migraine for 1 year of treatment.
	
Analysis of:
 
 • treatment-emergent adverse events (TEAEs) • discontinuation rates • vital signs and weight • electrocardiograms (ECGs) • laboratory measures • other safety parameters, including suicidality using the Columbia Suicide Severity Rating Scale (C-SSRS)

Secondary
 
 • To characterize the long-term pharmacokinetics, pharmacodynamics and immunogenicity of galcanezumab • To evaluate the long-term effectiveness of galcanezumab in the prevention of migraine 	
 • Assessment of serum concentrations of galcanezumab to enable a pharmacokinetic evaluation • Assessment of plasma concentrations of CGRP to enable a pharmacodynamic evaluation of target engagement of galcanezumab • Assessment of the development and consequences of ADA to galcanezumab in patients exposed to drug • Mean change from baseline (Visit 3) in the number of migraine headache days • Mean change from baseline in the number of headache days • Proportion of patients meeting 50% response criteria (reduction of at least 50% in the number of migraine headache days) • Mean change from baseline in PGI of illness as measured by PGI-S

Objectives	Endpoints

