5.2. Determination of Sample Size

Approximately 300 patients (approximately 150 patients per arm; approximately 240 patients with EM and approximately 60 patients with CM) will be enrolled for the purposes of regulatory registration, to ensure at least 100 patients per arm with 1 year of exposure. It is assumed that 30% of patients will not complete a 12-month treatment period.

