5.3.2. CM Patients

Patients meeting all eligibility requirements will be randomized to receive galcanezumab 120 mg/month, or galcanezumab 240 mg/month in a 1:1 ratio.

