5.8. Reports to be Generated at Interim and Final Database Lock

5.8.1. Report to be Generated at Interim Analysis

At the time of interim analysis, all randomized patients will have had the chance to complete Month 6 (Visit 10) in Study Period III. Analyses conducted at the interim analysis do not include any data from Study Period IV, unless otherwise specified. Efficacy/health outcome results are up to Month 6 data in SP III. Safety/protocol deviation results are based on all data during SP III.

For efficacy/health outcome analysis in SP III (continuous/binary outcomes using MMRM/GLIMMIX), overall (month 1-6) will be shown for treatment comparisons at the interim DBL instead of overall (month 1-12). They will be estimated as the main effect of treatment using Month 1 up to Month 6 data.

Disposition

- Patient Allocation by Investigator Site
- Summary of Patient Dispositions for Treatment Phase
- Listing of Subjects who discontinued for Treatment Phase or Post-Treatment Phase
- Listing of Patient Population by Treatment

Baseline Demographic

- Baseline Demographics and Disease Characteristics - Continuous Variables
- Baseline Demographics and Disease Characteristics - Categorical Variables
- Listing of Subjects Demographic

Efficacy/Health outcome

- Change from Baseline in the Number of Migraine Headache Days by 2 arms (CM120, CM240) using MMRM
- Change from Baseline in the Number of Migraine Headache Days by 2 arms (CM120, CM240) using MMRM (Figure)
- Descriptive Summary of Number of Migraine Headache Days (monthly raw values and change from baseline monthly values) by 6 arms (LY120/LY120, LY240/LY240, PLA/LY120, PLA/LY240, CM120, CM240)
- Descriptive Summary of Number of Migraine Headache Days (monthly raw values) by 6 arms (Figure)
- Descriptive Summary of Number of Migraine Headache Days (change from baseline monthly values) by 6 arms (Figure)
- Change from Baseline in the Number of Migraine Headache Days with Acute Medication Use by 2 arms (CM120, CM240) using MMRM
- Change from Baseline in the Number of Headache Days by 2 arms (CM120, CM240) using MMRM
- Distribution of Response Rates Based on Number of Migraine Headache Days by 2 arms (CM120, CM240) using GLIMMIX
- Distribution of Response Rates Based on Number of Migraine Headache Days by 2 arms (CM120, CM240) using GLIMMIX (Figure)
- Estimated Proportion of 50% Responders for Migraine Headache Days by 2 arms (CM120, CM240) using GLIMMIX

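### Adverse events are reported only as crude patient percentages under a one-year safety objective, with no exposure-adjusted or cumulative-incidence estimate despite 30% assumed non-completion and unequal interim follow-up

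*SAP*

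**What the plan says.** SAP Table CGAP. 4.1 gives the primary objective as "To evaluate the long-term safety and tolerability of galcanezumab 120 mg/month or 240 mg/month in patients with migraine for 1 year of treatment", with treatment-emergent adverse events (TEAEs) listed first among its endpoints. On sample size, section 5.2 states "Approximately 300 patients (approximately 150 patients per arm; approximately 240 patients with EM and approximately 60 patients with CM) will be enrolled", the purpose being "to ensure at least 100 patients per arm with 1 year of exposure". It adds: "It is assumed that 30% of patients will not complete a 12-month treatment period".

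For categorical variables without repeated measures, section 5.5.1 prescribes Fisher's exact test and names "Safety measures (including percentages of patients with TEAEs, SAEs, and AEs reported as a reason for discontinuation" as an example. Section 5.5.12.1 applies the test to Study Period (SP) III in the safety population and leaves SP IV descriptive. Section 5.5.12.1.1 and its subsections report numbers and percentages of patients; the six-arm TEAE tables carry no test.

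No AE rate per unit of person-time and no time-to-first-event or cumulative-incidence estimate is specified. Kaplan-Meier is planned only for loss of 50% response (section 5.5.10). Section 5.5.5 derives exposure in days, and section 5.5.11.3 reports migraine-related healthcare use per 100 patient-years.

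At the interim (section 5.8.1) every randomized patient has had the opportunity to reach Month 6. Efficacy is cut at Month 6, but "Safety/protocol deviation results are based on all data during SP III". The listed interim outputs include no exposure summary. At final lock (section 5.8.2) everyone has had the opportunity for 12 months.

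**The concern.** The objective names a one-year horizon, but the planned statistic has no time axis. A patient who leaves at Month 2 without an event stays in the denominator for all of SP III, although ten months went unobserved. The percentage therefore describes what was seen during the follow-up achieved, not what one year of treatment would bring.

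The interim is the more exposed case. One percentage pools patients with different lengths of follow-up, the analysis is meant to support a regulatory submission (section 5.6), and some interim analyses enter the final report (section 5.8.2). Without an exposure table among the listed outputs, a reader cannot turn those percentages into rates.

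Absolute incidences matter more than tests here. The study is open-label and has no untreated arm, and section 10.3.1 of the protocol addendum describes the chronic migraine (CM) analyses as descriptive in principle.

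**Working it through.** **The plan's own figure.** About 150 per arm with 30% non-completion gives 150 × 0.70 = 105 completers, which meets the target of at least 100. In reverse, 100 / 0.70 = 142.9, or 143 per arm, so about 150 is that minimum rounded up. The exposure target is consistent.

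**Inputs.** From the SAP: dropout d = 0.30 by 12 months; interim follow-up opportunity of at least 6 months, capped at 12 by the length of SP III. Assumed, because the documents are silent: true one-year risk r, event timing, dropout timing, and dropout independent of AEs.

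**Formula.** With f(t) the density of the first event and S(t) the probability of still being followed at time t (in years):

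crude = ∫₀¹ f(t) S(t) dt; relative shortfall = 1 − crude / r.

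For constant hazard, λ = −ln(1 − r).

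- Uniform dropout, S(t) = 1 − d·t: crude = r − d·[r/λ − (1 − r)]. Mean follow-up is 0.70 + 0.30 × 0.5 = 0.85 year.
 - r = 10%: λ = 0.1054; crude = 0.10 − 0.30 × (0.9491 − 0.90) = 8.53%; shortfall 14.7%.
 - r = 50%: λ = 0.6931; crude = 0.50 − 0.30 × (0.7213 − 0.50) = 43.4%; shortfall 13.3%.
- Exponential dropout, μ = −ln(0.70) = 0.3567: crude = λ/(λ+μ) × (1 − e^−(λ+μ)).
 - r = 10%: 0.2280 × 0.37 = 8.44%; shortfall 15.6%.

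**Other timings.** Front-loaded events are modelled with cumulative hazard proportional to t^0.5 or t^0.25. For the interim, S(t) is also multiplied by the probability that administrative follow-up reaches t. Relative shortfall against the true one-year risk:

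| Lock | Event timing | Dropout | r = 1% | r = 10% | r = 50% | r = 90% |
|---|---|---|---|---|---|---|
| Final | Constant | Uniform | 15.0% | 14.7% | 13.3% | 9.7% |
| Final | Constant | Exponential | 15.9% | 15.6% | 14.2% | 10.5% |
| Final | Constant | First 3 months | 26.2% | 26.1% | 25.1% | 22.0% |
| Final | Constant | Last 3 months | 3.7% | 3.6% | 2.8% | 1.2% |
| Final | t^0.5 | Uniform | 10.0% | 9.7% | 8.3% | 5.1% |
| Final | t^0.25 | Uniform | 6.0% | 5.8% | 4.7% | 2.4% |
| Final | t^0.25 | Last 3 months | 1.0% | 1.0% | 0.7% | 0.3% |
| Interim, follow-up uniform 6-12 months | Constant | Uniform | 33.7% | 32.8% | 28.0% | 17.1% |
| Interim, exactly 6 months for all | Constant | Uniform | 53.6% | 52.5% | 45.6% | 28.7% |

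**Effect on a dose comparison.** Take equal 36% risk (λ = 0.4463) and, as a pure illustration, exponential dropout of 20% in one arm and 40% in the other. The crude percentages are 32.5% and 28.7%, a difference of 3.8 points. The standard error of a difference near 31% is √(2 × 0.31 × 0.69 / n): about 6 points with 120 per EM (episodic migraine) arm and about 12 with 30 per CM arm.

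**What a rate would do.** Under constant hazard and independent dropout, first events divided by person-time estimate λ at either lock. For r = 10% that is 10.5 per 100 patient-years, whatever the dropout.

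**The case against.** The other side has several sound points.

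- A crude percentage is a legitimate incidence over SP III as observed. Events before leaving are counted, and the SAP never labels the percentage a one-year risk. This stands: the statistic is not wrong, only incomplete for the stated objective.
- A reader might infer that the plan understates one-year risk by about 15%. The documents do not support one figure. They give 30% as a planning assumption, with no timing, hazard shape or event rate, and a single number cannot cover both the interim and the final lock.
- A reader might also infer that the dose comparison is seriously biased. Section 5.5.1 compares doses within EM and within CM. If dropout is similar by arm the effect is small, and even the 20% versus 40% illustration moves the difference by less than one standard error.
- SP III and SP IV last 12 and 4 months, but the SAP does not compare their percentages.
- For AEs leading to discontinuation, the censoring argument does not carry over directly. At final lock the crude percentage is already the cumulative incidence in the presence of other exits.
- Exposure, doses received and disposition by visit are tabulated (sections 5.5.2 and 5.5.5), so differential dropout would be visible in the final report. Disposition is among the interim outputs; exposure is not.
- Some EM patients enter already treated in the parent study, so the pooled EM arms do not give a clean first-year risk by any method. This limits interpretation but does not favour the crude percentage.

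The allowance in section 5.5.1 for further exploratory analyses does not fill the gap, because it prespecifies nothing. Only the CM addendum of the protocol was available, but section 5.5 says that the SAP supersedes the protocol's statistical plans.

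**Conclusion.** The gap is real and bears on the primary objective: nothing in the plan estimates AE risk over one year in a way that accounts for follow-up time. With constant hazard and independent 30% dropout spread over the year, crude percentages at final lock would lie about 13-16% (relative) below the one-year risk, for risks up to 50%. Across the other assumed event and dropout timings the range is about 0.3% to 26%: smaller if events come early or dropout comes late, larger if dropout comes early. At the interim it is about 17-34% if follow-up is uniform over 6 to 12 months, and more if most patients are near 6 months. All of this assumes that leaving is unrelated to later AE risk, and that the 30% materializes.

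Absolute risks, EM versus CM displays and interim results are the ones affected. The point is worth acting on because the remedy is cheap, not because the planned tables are invalid.

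**What to change.** Keep the crude tables and add the following to sections 5.5.12.1.1 and 5.8:

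- **Rates.** First-event incidence per 100 patient-years by arm, for SP III, at the interim and final locks. Cover TEAEs overall, common preferred terms, serious AEs, and the three AE groups that the SAP singles out (hypersensitivity, injection site, upper respiratory tract infection). Person-time runs from the first CGAP injection to the first event or the end of SP III follow-up, whichever is earlier.
- **Cumulative incidence.** 12-month estimates for the main AE categories at final lock, from Kaplan-Meier with early leavers censored. For AEs leading to discontinuation, use cumulative incidence with other exits as competing events, not Kaplan-Meier.
- **Interim exposure.** Add an exposure-duration table to the interim outputs.
- **Wording.** Base any statement about one-year risk on these estimates, and describe the crude percentages as on-study incidence.

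The cost is a few extra tables programmed from AE dates and exposure data that the plan already uses. The downside is that a per-patient-year rate summarizes well only if the hazard is roughly constant, so it should be shown beside the cumulative incidence. The Kaplan-Meier estimates assume that leavers would have had the same later risk as those who stayed; say so in the table notes.
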